Important Study Contacts

Study Contact Name	Address	Telephone/Fax No.
Sponsor	PharmaMar SA [name]	Tel: [name] Fax: [name]
Sponsor Responsible Person	[name] Medical Affairs Manager International Associate Director [name]	Tel: [name] Fax: [name] Email: [contact]
Pharmacovigilance Contacts	Pharmacovigilance Department. Product Safety, PharmaMar [name]	Tel (24-hours): [name] Tel: [name] Fax: [name] Email: [contact]
	[name] Pharmacovigilance Technician	[contact] Email: [contact]
	[name] EEA QPPV Deputy and Drug Safety Physician	[contact] Email: [contact]
	[name] Drug Safety Physician	[contact] Email: [contact]
	[name], MD EEA Qualified Person for Pharmacovigilance and Senior Pharmacovigilance Manager	Tel (Madrid, Spain): [name] Tel (24-hours): [contact] [contact] Email: [contact]

Study Contact Name	Address	Telephone/Fax No.
Contract Research Organization (CRO)	Mapi, an ICON Plc Company (hereafter referred as Mapi) [name]	[contact]
Mapi Project Director	[name] [name].	[contact] Email: [contact]
Mapi Project Manager	[name] [name]	[contact] Email: [contact]
Coordinating Investigator	[name] Istituto Nazionale Tumori Pascale Napoli Italy	Email: [contact]

Synopsis

Study Title:	Non-interventional, multicenter, prospective, European study to describe the effectiveness of trabectedin + PLD in the treatment of relapsed ovarian cancer (ROC) patients by previous usage of an antiangiogenic drug
Protocol ID:	ET-D-031-14
Trial Centers:	Approximately 70 centers will be identified across 5 European countries (Italy, Spain, Germany, France, Belgium)
Study Objectives:	Primary Objective:
	To assess the progression-free survival (PFS) according to investigator criteria in relapsed ovarian cancer patients treated with trabectedin + pegylated liposomal doxorubicin (PLD) according to standard local clinical practice following approved Summary of Product Characteristics (SmPC) indication and dose, overall and by previous usage of antiangiogenic drug.
	Secondary Objectives:
	• To evaluate the response rates (complete response [CR] + partial response [PR]), and disease control rate (DCR; CR + PR + stable disease [SD])
	Overall survival (OS)
	To evaluate patient's performance status (PS)
	To assess treatment duration and number of cycles, treatment exposure, and time to next treatment
	To evaluate the safety of the combination of trabectedin + PLD
	Secondary objectives will be assessed overall and by previous usage of antiangiogenic drug.
Study Rationale:	To assess the PFS after trabectedin + PLD therapy for the treatment of relapsed ovarian cancer according to standard local clinical practice following approved SmPC indication and dose, while describing patients who were pretreated with an antiangiogenic drug and those not pretreated, in real-life clinical practice.
Study Design:	Non-interventional, multicenter, prospective study of trabectedin + PLD administered according to standard local clinical practice following approved SmPC indication and dose.

Study Population:	Patients with platinum-sensitive relapsed ovarian cancer who are receiving trabectedin + PLD according to standard local clinical practice following approved SmPC indication and dose.		
Selection Criteria:	 Women aged 18 years or older. Presence of platinum-sensitive relapsed ovarian cancer. Treatment indication according to local label SmPC and reimbursement for trabectedin and PLD treatment. Prior treatment with a minimum of 1 cycle of trabectedin + PLD before inclusion in the study. Written informed consent indicating that patients understand the purpose and procedures and are willing to participate in the study. 		
Study Drug:	Trabectedin (Yondelis®)		
Administration:	Trabectedin administered according to standard local clinical practice following approved SmPC indication and dose. The recommended dose of trabectedin for the treatment of relapsed platinumsensitive ovarian cancer is 1.1 mg/m² body surface area (BSA), administered every 3 weeks as a 3-hour infusion immediately after PLD 30 mg/m². Pretreatment with corticosteroids (e.g., dexamethasone) is required; additional anti-emetics may be administered in accordance with local practice, as needed, and as specified in the SmPC.		

Study Procedures:

Patients will be managed by their treating clinician without any additional instructions. The study will require no additional treatment procedures during patient visits.

Patients meeting the selection criteria will be invited to participate in the study. Before any study-specific data are recorded, patients will be provided with all the study details prior to their decision to participate and will be requested to sign an informed consent form (ICF) prior to their participation in the study.

Patient's baseline data, safety, and PS (evaluation according to the Eastern Cooperative Oncology Group [ECOG] score) will be collected during the Observation Period (treatment with trabectedin + PLD). Even though baseline data will be collected when patient is under treatment with trabectedin + PLD, it corresponds to data prior to treatment initiation. Response and survival assessments will be collected during the study and include symptomatic response and overall tumor response according to investigator criteria. The preferred method to measure overall response is Response Evaluation Criteria in Solid Tumors (RECIST) version 1.1 as it is the generally accepted standard criteria; however other criteria used by the investigators will be accepted.

Safety, response, reason for discontinuation of treatment and survival will be assessed during the follow-up period (1 month after the end the Observation Period and, for patients who discontinued trabectedin before the end of the 12-month Observation Period, 12 months after the Index date). Subsequent non-trabectedin treatments that the patient received during the follow-up period will also be described.

Study Endpoints:

Study endpoints will be assessed overall and by previous usage of antiangiogenic drug.

Primary endpoint:

PFS measured as time from first dose of trabectedin to disease progression as reported by the investigator or death regardless of cause.

Secondary endpoints:

- Response rate (CR+PR)
- DCR (CR+PR+SD)
- OS
- Evolution of the patient's performance status
- Treatment duration and number of cycles
- Treatment exposure
- Time to next treatment
- Safety of the combination of trabectedin + PLD

Safety Evaluation:	A solicited reporting system of adverse events (serious and non-serious, related or non-related) on trabectedin.		
Pharmacokinetic Considerations:	This is a non-interventional, prospective study and no pharmacokinetic or pharmacodynamic evaluations are planned.		
Planned Study Periods:	 Recruitment: 36 months Observation Period: up to 12 months Follow-up visits: 1 month after patient last on-study cycle and, for patients who discontinued treatment with trabectedin before the end of the 12-month Observation Period, 12 months after the index date. Data Base Lock: Nov 2019 Study Final Report: Jan 2020 		
Date Issued:	18 Nov 2014		
Date Amended:	18 September 2018		

18 September 2018 Confidential Trabectedin + PLD

List of Abbreviations

Abbreviation	Description
ADL	Activities of Daily Living
ADR	Adverse Drug Reaction
AE	Adverse Event
ALT	Alanine Aminotransferase
AST	Aspartate Aminotransferase
BSA	Body Surface Area
CI	Confidence Interval
CIOMS	Council for International Organizations of Medical Sciences
CR	Complete Response
CRF	Case Report Form
CRO	Contract Research Organization
CT	Computed Tomography
CTCAE	Common Terminology Criteria for Adverse Events
DCR	Disease Control Rate
DNA	Deoxy ribonucleic acid
ECOG	Eastern Cooperative Oncology Group
ESMO	European Society for Medical Oncology
eCRF	Electronic Case Report Form
EDC	Electronic Data Capture
EU	European Union
FAS	Full Analysis Set
FIGO	International Federation of Gynecology and Obstetrics
GCP	Good Clinical Practice
GVP	Good Pharmacovigilance Practices
h	Hour
HR	Hazard Ratio

Version 4- Amendement 2

Abbreviation	Description
IARC	International Agency for Research in Cancer
ICF	Informed Consent Form
ICH	International Conference on Harmonization
ID	Patient identification number for study participation
IEC	Independent Ethics Committee
IRB	Institutional Review Board
iv	Intravenous
kg	Kilogram
KM	Kaplan-Meier
m^2	Square Meter
MAH	Marketing Authorization Holder
MedDRA	Medical Dictionary for Regulatory Activities
mg	Milligram
MR	Magnetic Resonance
NCCN	National Comprehensive Cancer Network
ORR	Overall Response Rate
OS	Overall Survival
PD	Progression of Disease
PFS	Progression-Free Survival
PR	Partial Response
PS	Performance Status
q	Every
REB	Research Ethics Board
RECIST	Response Evaluation Criteria In Solid Tumors
RNA	Ribonucleic acid
SADR	Serious Adverse Drug Reaction
SAE	Serious Adverse Event
SD	Stable Disease

Abbreviation	Description
SmPC	Summary of Product Characteristics
US/USA	United States of America
VEGF	Vascular Endothelial Growth Factor
VS	Versus
WHO	World Health Organization
wk	Week

Table of Contents

Pı	:otocol/	Amendment Approval Page(s)	2
In	nportant	t Study Contacts	3
S	ynopsis		5
Li	ist of Al	bbreviations	9
Li	ist of Ta	ables	15
1	INT	RODUCTION	16

1 INTRODUCTION

1.1 Background

1.1.1 Ovarian Cancer

Ovarian cancer is a serious, clinically challenging malignancy with the majority of ovarian malignancies (85%-95%) developing from epithelial cells. Ovarian cancer represents a significant challenge in oncology, being a malignancy that has a mortality rate disproportionate to its incidence. According to the World Health Organization (WHO) International Agency for Research in Cancer (IARC) GLOBOCAN database, ovarian cancer comprised 3.6% of all incident cancer types reported worldwide in 2012, and 4.1% of cancer types across Europe. Yet despite its low incidence, ovarian cancer has the sixth highest cancer-related mortality rate in European women, and is associated with the highest mortality-to-case ratio of all gynecologic malignancies (Holschneider and Berek, 2000; World Health Organization, 2014).

A contributing factor to high mortality rates is the late disease diagnosis. Most women are asymptomatic until the disease has spread, with the majority of cases diagnosed at the advanced stage. In European countries, population-based data indicate that, of the subset of patients with known disease severity, 60% to 74% of cases of ovarian cancer are diagnosed at a FIGO (International Federation of Gynecology and Obstetrics) stage of III or IV (Maringe et al, 2012). Unfortunately, approximately 80% of patients will relapse after first-line platinum-based and taxane-based chemotherapy (National Cancer Institute, 2014). Given that relapsed ovarian cancer is not curable, most women who relapse die from their disease (Della Pepa and Banerjee, 2014). Consequently, developing new therapies for relapsed ovarian cancer is critical.

According to treatment guidelines from the National Comprehensive Cancer Network (NCCN) and European Society for Medical Oncology (ESMO), primary treatment for advanced ovarian cancer (FIGO stage II, III, IV) consist of surgical staging and cytoreductive surgery followed by a combination of platinum-based chemotherapy, including paclitaxel/carboplatin or docetaxel/carboplatin combination therapies, or bevacizumab-containing regimens (Colombo et al, 2010; National Comprehensive Cancer Network, 2014). According to ESMO clinical practice guidelines, the appropriate therapy for patients with relapsed ovarian cancer is guided by the time to progression since the last platinum-based treatment (referred to as the platinum-free interval). Patients who progress during platinum-based treatment are considered to have platinum-refractory disease, while patients who develop recurrence within 6 months from the completion of first-line platinum chemotherapy are considered to have platinum-resistant disease (Colombo et al, 2010). The prognosis for these patients is poor, with a median overall survival (OS) typically under 12 months. Treatment options include paclitaxel, pegylated liposomal doxorubicin (PLD), topotecan, and gemcitabine (Della Pepa and Banerjee, 2014). However, since response rates are only about 10%, the primary goal of therapy in these patients is palliative care (Colombo et al, 2010).

Patients with relapsed ovarian cancer who progress following an interval greater than 6 months since the last platinum-based treatment (platinum sensitive disease) have 2 categorizations: partially platinum-sensitive patients are those who progress between 6 and 12 months, while fully platinum-sensitive patients progress with a platinum-free interval of more than 12 months (Ledermann et al, 2013). Both types are likely to benefit from further platinum-based therapy. The ESMO clinical practice guidelines recommend that for partially platinum-sensitive and fully platinum-sensitive patients, carboplatin combination therapies are the treatment of choice (Ledermann et al, 2013). Platinum-containing regimens that are effective for these patients include carboplatin with paclitaxel, carboplatin with PLD, carboplatin with gemcitabine, and a combination of carboplatin with gemcitabine and the antiangiogenic agent bevacizumab (see Section 1.1.2) (Della Pepa and Banerjee, 2014; Gonzalez Martin et al, 2013). Surgical resection is also an option in platinum-sensitive patients with prolonged (over 24 months) treatment free-

interval, especially with isolated recurrence and good performance status (Colombo et al, 2010). However, no single therapeutic agent is recommended for relapsed ovarian cancer, and recurrence therapies may include drugs, radiation, or other treatments aimed at reducing tumor burden, control symptoms, or increase length and/or quality of life patients (National Comprehensive Cancer Network, 2014).

Compared with fully platinum-sensitive patients, partially platinum-sensitive patients have a lower response to platinum-based regimens, with shorter progression-free survival (PFS) and OS. Thus, different strategies beyond carboplatin-based regimens are needed. Based on a subgroup analysis of the open-label, multinational, multicenter, phase III OVA-301 study (see Section 1.1.3.1 for additional study details), both ESMO and The Spanish Research Group for Ovarian Cancer (GEICO) recommend the non-platinum-based regimen of trabectedin + PLD for patients with partially platinum-sensitive relapsed ovarian cancer (Gonzalez Martin et al, 2013; Ledermann et al, 2013).

1.1.2 Angiogenesis

Angiogenesis is a key factor contributing to tumor growth and metastases. Since neoplasms are dependent, in part, on the formation of adequate vascular support, there is a focus on therapies targeting angiogenesis to reduce the growth and spread of ovarian cancer. For patients with ovarian cancer, the clinical utility of antiangiogenic therapies is apparent, since the extent of angiogenesis correlates inversely with prognosis (Huang et al, 2000).

Studies have demonstrated a complex relationship underlying angiogenesis and vascular endothelial growth factor (VEGF), a family of ligands that are often overexpressed in women with ovarian cancer, and is an independent prognostic factor for OS (Aravantinos and Pectasides, 2014). Thus, many current therapeutic approaches target the inhibition of VEGF and its receptors (Eisenhauer et al, 2012). Current VEGF-mediated antiangiogenic therapies include biologics that target the ligand, including bevacizumab and aflibercept, and tyrosine kinase inhibitors that target VEGF receptors, such as pazopanib, cediranib, sorafenib, and vandetanib (Slomovitz et al, 2011).

1.1.3 Trabectedin + Pegylated Liposomal Doxorubicin (PLD)

Trabectedin combined with PLD is approved in the EU for the treatment of relapsed platinum-sensitive ovarian cancer. Trabectedin (Yondelis®) is a novel antitumor agent derived from a marine source, the Caribbean tunicate *Ecteinascidia turbinata* and currently produced synthetically (Pommier et al, 1996). Trabectedin is a first-in-class antitumor agent with a complex mechanism of action at the level of gene transcription. Trabectedin binds covalently to the minor deoxyribonucleic acid (DNA) groove and alkylates the N2 amino group of a guanine residue, which bends towards the major groove (Pommier et al, 1996). Cytotoxic concentrations of trabectedin delay cell cycle progression through the S phase and produces arrest at G2/M, ultimately resulting in p53-independent apoptosis (Carter and Keam, 2007; Erba et al, 2001; Martinez et al, 2001; Martinez et al, 2005).

Trabectedin also has selective anti-inflammatory and immunomodulatory properties that affect the tumor microenvironment. Emerging evidence suggests trabectedin has selective cytotoxicity on tumor stroma macrophages, inhibits VEGF, and selectively inhibits inflammatory mediators. These actions collectively inhibit tumor growth, invasion and metastases, while also providing an antiangiogenic effect (Poveda et al, 2014).

PLD is available as doxorubicin hydrochloride in a pegylated liposomal formulation. Pegylation involves encapsulated doxorubicin hydrochloride in liposomes with surface-bound methoxypolyethylene glycol. This process protects liposomes from an immune response, thereby increasing its blood circulation time.

The active ingredient of PLD—doxorubicin hydrochloride—is a cytotoxic anthracycline antibiotic obtained from *Streptomyces peucetius* var. *caesius*. Although the exact mechanism of action is not known, it is generally believed that inhibition of DNA, ribonucleic acid (RNA), and protein synthesis is responsible for the majority of antitumor effects of PLD. This is probably the result of intercalation of the anthracycline between adjacent base pairs of the DNA double helix thus preventing their unwinding for replication. (Caelyx SmPC, 2006)

The recommended dosage for trabectedin in relapsed ovarian cancer is 1.1 mg/m² administered as a 3-hour infusion every 3 weeks (3h q3w), immediately after infusion of 30 mg/m² PLD.

1.1.3.1 **Efficacy**

Several phase I trials extensively evaluated the safety and antitumor activity of trabectedin in patients with advanced solid malignancies using different rates of intravenous (iv) infusion on every-3-week (q3w) schedules (Ryan et al, 2001; Taamma et al, 2001; Twelves et al, 2003; van Kesteren et al, 2000; van Kesteren et al, 2002). In these phase I trials, trabectedin produced objective antitumor responses in heavily-pretreated patients with diverse tumor types.

A retrospective pooled analysis of 3 phase II studies evaluated the efficacy and safety profile of trabectedin monotherapy as a second- and third-line therapy in patients with relapsed ovarian cancer (del Campo et al, 2013). Three trabectedin dose schedules were investigated: 1.3 mg/m² 3h q3w administered to 94 patients, 0.58 mg/m² given to 147 patients as a 3-hour weekly infusion for 3 weeks of a 4-week cycle (3h qw x 3 q4w), and 1.5 mg/m² over 24 h every 3 weeks (24h q3w) administered to 54 patients. Of the combined total of 295 patients, 189 (64%) had platinum-sensitive disease. The primary endpoint in all 3 trials was the overall response rate (ORR, complete response [CR] + partial response [PR]). Among the secondary endpoints was the disease control rate (DCR), defined as the percentage of patients with a CR or PR and/or stable disease (SD) lasting 3 months or more. Compared with the weekly schedule, both q3w regimens showed a significantly higher ORR (36% vs 16%, P < 0.001) and DCR (66% vs 46 %, P < 0.001), and a longer median PFS (5.6 vs 2.8 months, P < 0.0001). Patients with platinum-sensitive disease treated with either q3w schedule had a longer median PFS (24h, 6.2 months; 3h, 6.8 months) versus (vs) the weekly schedule (5.1 months). The median OS for the a3w schedules was also comparable (24h, 20.4 months; 3h, 17.1 months) and longer than the weekly regimen (13.7 months). Patients with platinum-sensitive disease also had a higher median OS (20.4 months) compared with platinum-resistant patients (11.1 months). The analysis demonstrated that trabected in was an effective monotherapy for the treatment of relapsed ovarian cancer, with better outcomes in patients with platinum-sensitive disease. Given the better safety profile regarding neutropenia, fatigue, and vomiting for the 3h q3w vs the 24h q3w schedule, the 3h q3w schedule (associated with shorter infusion times) was considered the most appropriate regimen.

The key evidence of efficacy of trabectedin + PLD in relapsed ovarian cancer is based on an open-label, multicenter, randomized, phase III study (OVA-301) in 672 patients who experienced either persistent or recurrent disease, or disease progression following a prior platinum-based chemotherapy. Patients also had measurable disease according to the Response Evaluation Criteria in Solid Tumors (RECIST) and an Eastern Cooperative Oncology Group (ECOG) performance status (PS) of 2 or less. The randomization was stratified according to whether the patient had platinum-sensitive disease or platinum-resistant disease (Poveda et al, 2014). Treatment groups included trabectedin 1.1 mg/m² administered as a 3-hour infusion and PLD 30 mg/m² administered as a 1.5-hour infusion every 3 weeks, or PLD 50 mg/m² administered as a 1.5-hour infusion every 4 weeks. The primary analysis of PFS by independent radiology review was performed on 645 patients. Median PFS for the trabectedin + PLD group (7.3 months) vs PLD alone (5.8 months) translated to a 21% risk reduction for disease progression (Hazard ratio [HR] = 0.79,

95% CI: 0.65-0.96). Secondary analyses of ORR also favored the combination arm (HR = 1.65, 95% CI: 1.14-2.37). In patients with platinum-sensitive relapsed ovarian cancer (65% in trabectedin + PLD; 63% in PLD arm), median PFS was 9.7 months in the trabectedin + PLD arm compared with 7.2 months in the PLD monotherapy arm (HR = 0.66, 95% CI: 0.52-0.85).

A secondary analysis of 214 partially platinum-sensitive patients from the OVA-301 study demonstrated a 35% risk reduction of disease progression or death that significantly favored the trabectedin + PLD combination (HR, 0.65. 95% CI, 0.45-0.92). The trabectedin + PLD group had a median PFS of 7.4 months vs 5.5 months for PLD monotherapy. When PFS results were compared across subsets of patients according to patients' platinum-free interval, the largest benefit with trabectedin + PLD treatment was obtained with partially platinum-sensitive patients (Poveda et al, 2011).

The protocol-defined analysis of OS for OVA-301 did not demonstrate differences across treatment groups: the median OS was 22.2 months for trabectedin + PLD and 18.9 months for PLD (HR = 0.86, P = 0.08). However, a significant imbalance of the platinum-free interval across treatment groups (trabectedin + PLD, mean PFI = 10.6 months; PLD, mean PFI = 13.3 months; P < 0.01) spurred an exploratory multivariate analysis that considered platinum-free interval and other prognostic factors as covariates, which demonstrated a significant OS advantage in favor of trabectedin + PLD (22.6 vs 19.4 months; HR = 0.82, 95% CI: 0.69-0.98). Further analysis with 430 platinum-sensitive patients showed a median OS of 27.0 months for trabectedin + PLD and 24.1 months for PLD (HR = 0.83; 95% CI: 0.67-1.04). For partially platinum-sensitive patients, the median OS of 22.4 months in the trabectedin + PLD group was significantly longer than in the PLD group at 16.4 months (HR = 0.64; 95% CI: 0.47-0.86) (Monk et al, 2012; Poveda et al, 2014).

Further advantages to OS were demonstrated in a subgroup of 94 patients with partially platinum-sensitive disease from the OVA-301 trabectedin + PLD arm who subsequently received platinum-based chemotherapy at progression. Compared with PLD alone, trabectedin + PLD (followed by subsequent platinum-based therapy) induced a 9-month longer median OS (27.7 vs 18.7 months) and a significant 42% decrease in the risk of death (HR = 0.58; P = 0.0153) (Poveda et al, 2014).

Thus, the OVA-301 trial demonstrated a clinical benefit of trabectedin + PLD compared with PLD alone in patients with platinum-sensitive relapsed ovarian cancer.

1.1.3.2 **Safety**

Myelosuppression, elevated alanine aminotransferase (ALT) and aspartate aminotransferase (AST), and fatigue were the primary dose-limiting toxicities in the dose-finding phase I studies.

Adverse events from the OVA-301 trial, 1 dose-ranging randomized control trial, and 2 nonrandomized trials reported rates of grade 3 (severe) and 4 (life-threatening) adverse events of 89% vs 58% for trabectedin + PLD compared to PLD alone, respectively. The rates of discontinuation due to adverse events were 17% vs 9%, for patients who received trabectedin + PLD vs patients receiving PLD alone (Papaioannou et al, 2011). Adverse events from OVA-301 were collected from 333 patients receiving trabectedin + PLD and 330 patients receiving PLD alone. The most frequent grade 4 hematologic adverse events at least possibly related to treatment with trabectedin + PLD vs PLD included neutropenia (34% vs 8.5%), leukopenia (8.4% vs 2.4%), thrombocytopenia (8.1% vs 0.6%), anemia (3.0% vs 0.3%), and febrile neutropenia (2.4% vs 0.3%). The most frequent grade 4 nonhematologic adverse events that were more common with trabectedin + PLD therapy included increases in ALT (2.4% vs 0%) and AST (0.9% vs 0.3%). The most common adverse events leading to treatment termination or dose adjustment was neutropenia for trabectedin + PLD and hand-foot syndrome for PLD (Monk et al, 2010).

All patients must receive corticosteroids (e.g., 20 mg dexamethasone iv) 30 minutes prior to PLD (in combination therapy) or Yondelis (in monotherapy); not only as anti-emetic prophylaxis, but also because it appears to provide hepatoprotective effects. Additional anti-emetics may be administered as needed (Yondelis SmPC).

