8 SAFETY REPORTING

8.1 Definitions

8.1.1 Adverse Event (AE)

An adverse event (AE) is defined as any untoward medical occurrence in a patient or clinical trial subject administered a medicinal product that does not necessarily have a causal relationship with treatment [Directive 2001/20/EC Art 2(m)]. An adverse event can therefore be any unfavorable and unintended sign (e.g., an abnormal laboratory finding), symptom, or disease temporally associated with the use of a medicinal product, whether or not it is considered related to the medicinal product.

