8.2 Collection and Reporting of Safety Information for Study Investigators

A solicited reporting system of all Adverse Events (serious and non-serious, related and not-related) will be used during this study, from the beginning of trabectedin + PLD treatment. Whenever possible the investigator will record the diagnosis instead of the signs and symptoms.

To properly classify each adverse event, the treating physician should assess seriousness, causal relationship to study drugs (trabectedin + PLD), and severity (grade).

Seriousness assessment will take into account criteria described in Section 8.1.2.

The investigators must provide an assessment of the causal relationship for all AEs with the study treatment according to the following scale:

- Related (Y): there is a reasonable possibility that the study treatment caused the AE (i.e., an ADR).
- Not related (N): there is no reasonable possibility that the study treatment caused the AE and other causes are more probable.
- Unknown (Unk): Only to be used in exceptional situations where the investigator has insufficient information (i.e., the patient was not seen at his/her center) and if none of the above can be used

The grade will be assessed by the investigator according to the Common Terminology Criteria for Adverse Events (CTCAE Version 4.0) in force at time of study database development. The CTCAE displays Grades 1 through 5 with unique clinical descriptions of severity for each AE based on this general guide:

- Grade 1 = mild; asymptomatic or mild symptoms; clinical or diagnostic observations only; intervention not indicated
- Grade 2 = moderate; minimal, local or non-invasive intervention indicated; limiting ageappropriate instrumental activities of daily living (ADL)¹
- Grade 3 = severe or medically significant but not immediately life-threatening; hospitalization or prolongation of hospitalization indicated; disabling; limiting self-care ADL²
- Grade 4 = life-threatening consequences; urgent intervention indicated
- Grade 5 = death related to AE

Instrumental ADL refer to preparing meals, shopping for groceries or clothes, using the telephone, managing money, etc.

² Self-care ADL refer to bathing, dressing and undressing, feeding self, using the toilet, taking medications, and not bedridden.

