3.2 Sample Size

At least 300 patients are to be selected. With this number it is judged that PFS after treatment with trabectedin + PLD will be estimated with sufficient accuracy.

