9.5 Safety Analyses

9.5.1 Adverse Events

A solicited reporting system of AEs (serious and non-serious, related and not related) was used during this study, from the beginning of trabectedin + PLD treatment.

Whenever possible the investigator recorded the diagnosis, classified each adverse event in regards of seriousness and causal relationship to study drugs (trabectedin + PLD), and reported severity (grade).

AEs will be coded in the Medical Dictionary for Regulatory Activities (MedDRA) version 17.0 or higher by system organ class and a preferred term. Each event will be graded according to medical record documentation as 1 = mild, 2 = moderate, 3 = severe, 4 = disabling or life threatening consequences, and 5 = death.

The descriptive summaries presenting treatment emergent AEs will include AEs reported from Day 1 of study treatment to 30 days post last dose of study treatment. AE summaries will use the patient's maximum severity reported for each system organ class and preferred term. The corresponding summaries will be presented for AEs and SAEs grade 3 or higher.

Patient incidence of adverse drug reactions (ADR) related to trabectedin and related to PLD, respectively, will be tabulated by system organ class, preferred term and severity grade for all drug reactions and serious drug reactions. The corresponding summaries will be presented for ADRs and SADRs grade 3 or higher. ADR's relationship to treatment reported as unknown will be assumed to be related to both trabectedin and PLD.

In addition, and complementing the summaries above, AEs, SAEs, ADRs and SADRs will also be summarized by preferred term only, and in descending order of frequency.

A summary table will also be produced summarizing all event summaries and will include, AEs, SAEs, ADRs, SADRs, those leading to treatment discontinuation, and fatal events on study.

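### The SAP defines no grouped terms for the main known toxicities, so single preferred-term rows may understate them if sites word the same event differently

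*Protocol*

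**What the plan says.** Protocol 1.1.3.2 (Safety) identifies myelosuppression, transaminase rises and fatigue as the dose-limiting toxicities of the phase I studies. It then gives grade 4 rates, for events at least possibly related to treatment, from the phase III trial of the combination against PLD alone: "neutropenia (34% vs 8.5%), leukopenia (8.4% vs 2.4%), thrombocytopenia (8.1% vs 0.6%), anemia (3.0% vs 0.3" (percent). This is background and sets no counting rule for the present study.

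The rules that matter here are these:

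- Protocol 8.1.1 includes in the definition of an adverse event "any unfavorable and unintended sign (e.g., an abnormal laboratory finding".
- Protocol 8.2 instructs: "Whenever possible the investigator will record the diagnosis instead of the signs and symptoms".
- SAP 9.5.1 on coding: "AEs will be coded in the Medical Dictionary for Regulatory Activities (MedDRA) version 17.0 or higher by system organ class and a preferred term".
- SAP 9.5.1 on counting: summaries use each patient's "maximum severity reported for each system organ class and preferred term".
- SAP 9.5.1 on ranking: AEs, SAEs, ADRs and SADRs are also to be "summarized by preferred term only, and in descending order of frequency".

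SAP 11.1 lists the matching tables, none of which has a grouped row. It also lists laboratory tables for haemoglobin, absolute neutrophil count, platelets, AST, ALT and other tests, and a table of clinically significant results. SAP 9.5.3 describes the laboratory data behind them.

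**The concern.** A low neutrophil count can enter the database as a diagnosis or as a laboratory finding. The instruction to prefer the diagnosis reduces this, but it is conditional and says nothing specific about low counts or raised enzymes. About 70 sites in five countries will apply it. If the two wordings receive different preferred terms, a patient recorded under only one of them appears in only one row, and no planned AE or ADR table then gives the number of patients with low neutrophils under either wording.

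The safety of the combination is a stated secondary objective, overall and by previous antiangiogenic use. The figures at risk are the per-toxicity incidences for the regimen's best-known toxicities and their position in the frequency ranking.

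**Working it through.** **Inputs**

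- Reference rates: Protocol 1.1.3.2, as quoted above. Denominators: "Adverse events from OVA-301 were collected from 333 patients receiving trabectedin + PLD and 330 patients receiving PLD alone".
- Study size: SAP 3.2, "At least 300 patients are to be selected". N = 300 is used.
- Share *s* of affected patients who have the second term: not in the documents. Assumed range 0 to 50%.
- That the two wordings code to different preferred terms: assumed. The documents do not show how individual terms are placed in the dictionary.

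The plan states no figure of its own on this point, so there is nothing to reproduce.

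**Step 1. Are the background rates internally consistent?** Yes; whole-number counts match them.

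- Neutropenia: 112 to 114 of 333 rounds to 34%; 28/330 = 8.5%.
- Leukopenia: 28/333 = 8.4%; 8/330 = 2.4%.
- Thrombocytopenia: 27/333 = 8.1%; 2/330 = 0.6%.
- Anemia: 10/333 = 3.0%; 1/330 = 0.3%.

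**Step 2. Split with no patient having both terms.** Take a true rate of 34%: 0.34 × 300 = 102 patients. The larger row holds 102 minus the rounded value of 102*s*. Intervals are exact (Clopper-Pearson) 95%.

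| *s* | Larger row | Rate (95% CI) | Other row |
|---|---|---|---|
| 0% | 102 | 34.0% (28.7 to 39.7) | 0 |
| 10% | 92 | 30.7% (25.5 to 36.2) | 10 (3.3%) |
| 20% | 82 | 27.3% (22.4 to 32.8) | 20 (6.7%) |
| 30% | 71 | 23.7% (19.0 to 28.9) | 31 (10.3%) |
| 50% | 51 | 17.0% (12.9 to 21.7) | 51 (17.0%) |

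A grouped term that counts each patient once gives 34.0% (28.7 to 39.7) at every *s*. For thrombocytopenia (24 of 300, 8.0%) the larger row falls to 17 (5.7%) at a 30% split and 12 (4.0%) at 50%.

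**Step 3. Can the two rows be added afterwards?** Only if no patient has both terms. Let a share *o* of the patients with the second term also have the first:

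- row 1 = 34% × [1 − *s*(1 − *o*)]
- row 2 = 34% × *s*
- sum = 34% × (1 + *so*)

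With *s* = 0.3 and *o* = 0.5, row 1 = 34 × 0.85 = 28.9%, row 2 = 34 × 0.3 = 10.2%, and the sum is 39.1% against a true 34%.

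**Step 4. Ranking.** The reference counts for leukopenia and thrombocytopenia are 28 and 27. Moving two leukopenia patients to another term gives 26 against 27 and reverses the order.

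**Step 5. Do other planned outputs supply the missing count?**

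- System organ class rows: if the two wordings fall in different classes, neither row captures both. If they fall in the same class, its row also contains every other event in that class. Neither case gives a count for the single toxicity.
- Overall AE, SAE, ADR and SADR summary: not affected by a split, but it identifies no toxicity.
- Laboratory tables (SAP 9.5.3, 11.1): independent of the AE wording, but they use whatever tests usual practice provides. In follow-up they cover only tests linked to adverse events. They assign no relatedness, state no CTCAE grading and leave clinical significance undefined. No white cell count table is listed, so leukopenia is not covered.

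**The case against.** The strongest reply is that splitting is not shown. The recording rule favours the diagnosis, grading by CTCAE v4.0 under Protocol 8.2 also encourages uniform terms, and the documents do not say how the dictionary places any pair of wordings. At a zero split nothing is lost. Both rows would appear in the same table, grouped counts can be derived from the coded data at any time, and the table shells are in a separate document. The ANC, platelet, haemoglobin, AST and ALT tables do not depend on the AE term. All of this is correct, and it confines the point to a possible understatement in single-term rows.

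The reply does not remove the gap. The diagnosis rule is conditional, the laboratory tables cannot give a related, graded incidence, and a term list drawn up after the counts are known is open to selection.

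A reader might go further and infer any of the following. The documents do not support them.

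- *That the toxicities are in fact split and every preferred-term and class table reads too low.* No split share is given, and a patient missing from one row raises another.
- *That comparison with the phase III rates is invalid.* No such comparison is planned, and the protocol does not say whether those rates were single-term or grouped.
- *That the antiangiogenic groups will differ through wording alone.* This needs wording to vary by centre and centre to be associated with prior antiangiogenic use. Neither is documented.

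**Conclusion.** The point holds as a gap in specification. Neither the protocol nor the SAP defines grouped terms for the main known toxicities, while the reporting rules allow one event to be recorded in two forms. Single-term rows may therefore understate these toxicities.

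For a true 34% in 300 patients, the understatement runs from 0 points with no split to 17 points at an even split without overlap; at a 30% split it is 34.0 − 23.7 = 10.3 points. The size depends wholly on an assumed split share and on the assumption that the wordings code to different preferred terms. The overall AE and ADR summaries are unaffected. Tabulation by class and preferred term is not an error in itself. Importance is minor to moderate, because the safety analysis is descriptive and secondary.

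**What to change.** In SAP 9.5.1 and 11.1, before database lock:

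- List grouped terms for neutropenia, leukopenia, thrombocytopenia, anemia and ALT/AST increase, taken from the MedDRA version in use. Keep febrile neutropenia separate.
- Count each patient once per group at worst grade, for AEs, SAEs and ADRs.
- Show these rows beside the preferred-term tables, which stay as planned.
- State that the grouped rows are to be read with the laboratory tables, and note the limits of those tables.

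The cost is a short term list and some extra rows; no new data are needed. Reported incidences for the grouped toxicities may be somewhat higher than the single-term rows, and the report should say why.
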